6.3. Handling of Dropouts or Missing Data

For CGM outcome variables only derived for Visit 3 (baseline) and Visit 14 (endpoint) based upon the CGM data, missing data will not be addressed. Only completers will be included in ANCOVA analysis.

For continuous variables collected at baseline and at Visit 14, missing data will not be addressed. Only completers will be included in ANCOVA analysis.

For continuous longitudinal variables collected at baseline and more than one scheduled post-baseline visits according to SoA in Section 1.3, missing data will be addressed by using a MMRM analysis. The MMRM model provides consistent estimator when data is missing at random. The model implicitly adjusts for missing data through a variance-covariance structure.

6.4. Multiple Comparisons/Multiplicity

Comparison between baseline and endpoints will be performed at the full significance level of 0.05. No multiplicity adjustment will be made.

6.5. Patient Disposition

Patient disposition will be displayed in a flowchart showing the number of patients entered, enrolled, treated, and discontinued across all study periods.

Frequency counts and percentages of the Treated Population completing and discontinuing from the study will be presented. Reasons for discontinuation from the study and study treatment will be summarized.

Frequency counts and percentages of all patients entered, enrolled, and discontinued from the study during the lead-in period will be summarized. Reasons for discontinuation during

screening will be summarized for the Entered Population. Reasons for discontinuation from the study during the lead-in period will be summarized for the Enrolled Population.

A listing of the primary reason for study/treatment discontinuation will be generated for the Enrolled Population.

A listing will be generated for the Treated Population, including the following variables but not limited to: investigator ID, patient ID, date of signature of informed consent form, first and last dose date of Humalog in the lead in period, study treatment assignment date, first and last dose date of LY900014 in the treatment period (titration and maintenance periods).

6.6. Patient Characteristics

A summary table will be generated for patient characteristics at study entry using the Treated Population. The following variables will be included but not limited to: age, age groups (<40 and ≥ 40 years, and <65, ≥ 65 years), sex, ethnicity, race, height, weight, body mass index (BMI), BMI groups (<25, ≥ 25 to <30, ≥ 30 to <35, and ≥ 35 kg/m²). For continuous variables, the following statistics will be provided: mean, SD, minimum, maximum, and median. For categorical variables, summary statistics will include sample size, frequency, and percentage. A listing of patient characteristics at baseline will be provided.

A similar summary of diabetes characteristics will also be generated. The following variables will be included but not limited to: duration of diabetes, percentage of time with CGM values from 70 to 180 mg/dL over the lead in period, HbA1c at study entry.

For the Treated Population, the number and percentage of patients with historical conditions will be summarized using Medical Dictionary for Regulatory Activities (MedDRA) Preferred Term (PT) (without regard to System Organ Class [SOC]), and the number and percentage of patients with preexisting conditions will also be summarized using MedDRA PT (without regard to SOC). Historical conditions are conditions that end prior to informed consent and preexisting conditions are conditions that are still ongoing at informed consent. Events will be ordered by decreasing frequency.

6.7. Treatment Compliance

No analysis for treatment compliance is planned for this study.

6.8. Concomitant Therapy

Concomitant medications will be summarized for the Treated Population for Titration and Maintenance periods combined. The percentages of patients receiving each concomitant medication will be summarized by treatment using PT nested within Anatomical Therapeutic Chemical (ATC) Level 3 code. Medications will be ordered by decreasing frequency within ATC level. Concomitant medication used during the lead-in period will also be summarized for the Enrolled Population.

6.9. Efficacy Analyses

6.9.1. Primary Outcome and Methodology

The primary objective of this study is to evaluate the percentage of time with glucose values within target range (70 to 180 mg/dL, both inclusive) after 35 days of using the study titration scheme with LY900014 treatment and degludec. Both actual and change from baseline will be derived and analyzed by the ANCOVA model as described in Section 6.1.

The primary analyses will be conducted on the Treated Population based upon the CGM data collected for Visit 3 (baseline) and Visit 14 (endpoint), excluding data (if any) that are collected while patients are temporarily off Humalog during the lead-in period or temporarily off IP during the maintenance period. Comparison between baseline and endpoints will be performed at the full significance level of 0.05.

Derivation and analysis of primary endpoint (derived for 24-hour, daytime and nighttime and by-meal) and other CGM endpoints are described in Section 6.13.

6.9.2. Other Secondary Efficacy Analyses

The analyses described in Section 6.9.2 will include data collected from the Treated Population. Details for the CGM analyses are described in Section 6.13. Continuous secondary efficacy variables, as well as the change from baseline for these variables, will be analyzed by the MMRM or ANCOVA model as described in Section 6.1.

The ICR data from the day before a scheduled visit will be transcribed in eCRF at Visit 2, Visit 3 through Visit 14 and ET Visit, respectively. Any changes and associated to meals for ICR during the Treatment period will be captured. A listing will be provided to include ICR data collected at Visit 2, changes in ICR by meal captured during Treatment period in the eCRF. An MMRM model similar to that for the primary endpoint will be used to analyze actual and change from baseline in ICR.

For the following secondary efficacy endpoints data collected for Visit 3 (baseline) and Visit 14 (endpoint), an ANCOVA model as described in Section 6.1 will be used:

- actual and change from baseline in insulin doses, including mean total daily basal (U/day, U/kg/day), mean total daily bolus (U/day, U/kg/day), and mean total daily insulin dose (U/day, U/kg/day) and mean total daily bolus / total daily insulin dose ratios (%)

The investigator will transcribe the Humalog dose at Visit 3 (data from Day -10 to Day -1) and LY900014 dose at Visit 14 (data from Day 36 to Day 45) to eCRF. To assess the insulin doses over the course of 10 days for each visit, the mean total daily basal dose will be derived based on CGM data collected during lead in period (data from Day -10 to Day -1) and maintenance period (data from Day 36 to Day 45), and mean total bolus doses will be derived based upon the eCRF data collected at Visit 3 and Visit 14.

Relationships between ICR and TDD will be evaluated through regression lines (ICR versus 1/TDD) and compared with the “500 Rule,” which is currently used in clinical practice where

ICR = 500/TDD (Section 2.1 in study protocol) by visit. Regression lines with and without intercept will be analyzed. The analyses will be conducted based upon ICR and mean total daily insulin dose (U/day) collected for Visit 3 and Visit 14, separately.

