2.3.3. Overall Benefit: Risk Conclusion

Considering the measures taken to minimize risk to participants involved in this study, the potential risks identified in association with LY900014 are justified by the potential benefits that may be afforded to participants with T1D.

3. Objectives and Endpoints

Objectives	Endpoints
Primary	
To evaluate the time that glucose values are within the target range 70 to 180 mg/dL from CGM use, after 35 days of using the study titration scheme with LY900014 treatment and degludec	Percentage of time with sensor glucose values between 70 and 180 mg/dL (both inclusive), with CGM use during the maintenance period
Secondary	
To evaluate ICR with LY900014 treatment	ICR at the end of the maintenance period
To evaluate the relationship between ICR and TDD with LY900014 treatment	ICR×TDD for the maintenance period
To evaluate total daily, basal, and prandial insulin dose with LY900014 treatment and degludec	Prandial: TDD ratio for the maintenance period
Tertiary/Exploratory	
To evaluate the safety of LY900014	Adverse events and vital signs
To explore the relationship between 
 • ICR and TDD • ISF and TDD • ICR and ISF with LY900014 treatment	
 • Slope of the linear regression line of ICR or ISF on the reciprocal of TDD • Slope of the linear regression line of ICR on ISF, for the maintenance period
To explore ISF with LY900014 treatment	ISF at the end of the maintenance period
To explore glucose profiles, obtained from CGM use with LY900014 treatment	Actual and change from baseline in mean sensor glucose with CGM use during the maintenance period
To explore highest PPG level within 4 hours* after meal(s), obtained from CGM use, with LY900014 treatment	Actual and change from baseline in highest PPG level within 4 hours after meal(s), with CGM use during the maintenance period

Objectives	Endpoints
To explore the time from start of meal to highest PPG level within 4 hours* after meal(s), obtained from CGM use, with LY900014 treatment	Actual and change from baseline in minutes from start of meal to highest PPG level within 4 hours after meal(s), with CGM use during the maintenance period
To explore the percentage of time spent in hypoglycemic glucose ranges, obtained from CGM use, with LY900014 treatment	Actual and change from baseline in percentage of time with sensor glucose values <54 mg/dL, with CGM use during the maintenance period

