9.1. Statistical Hypotheses

As an exploratory pilot dose optimization study, the primary objective of Study ITSZ is to evaluate the percentage of time with glucose values within target range (70 to 180 mg/dL, both inclusive) after 35 days of using the study titration scheme with LY900014 treatment and degludec.

The study will investigate if a more aggressive ICR is needed with LY900014 treatment for participants to reach the study-specific glucose target, compared to the “500 Rule” that is currently used in clinical practice.

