9.4.3. Secondary Endpoint(s)

Additional continuous secondary efficacy variables, as well as the change from baseline for these variables, will be analyzed by the MMRM or ANCOVA model as described in Section 9.4.1.

Relationships between ICR and TDD will be evaluated through regression lines (ICR versus 1/TDD) and compared with the “500 Rule,” which is currently used in clinical practice where ICR = 500/TDD (Section 2.1).

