6.9.1. Primary Outcome and Methodology.....	17
6.9.2. Other Secondary Efficacy Analyses	17
6.9.3. Exploratory Efficacy Analyses	18
6.10. Safety Analyses.....	18
6.10.1. Extent of Exposure.....	18
6.10.2. Adverse Events	19
6.10.3. Hypoglycemic Events and Other Adverse Events.....	20
6.10.3.1. Hypoglycemia	20
6.10.3.2. Injection Site Reaction.....	21
6.10.4. Clinical Laboratory Evaluation.....	21
6.10.5. Vital Signs and Other Physical Findings.....	21
6.10.6. Patient Narratives.....	22
6.11. Important Protocol Deviations.....	22
6.12. Interim Analyses and Data Monitoring.....	22

6.13. CGM Analyses.....22

6.14. Clinical Trial Registry Analyses.....25

7. Unblinding Plan27

8. References28

9. Appendices29

Table of Contents

Table		Page
Table ITSZ.4.1.	Objectives and Endpoints.....	8
Table ITSZ.6.1.	Patient Populations	12
Table ITSZ.6.2.	Baseline and Post-Baseline Definitions and Patient Population by Study Period and Type of Analysis.....	14
Table ITSZ.6.3.	Adverse Event Analysis Periods	20
Table ITSZ.6.4.	Summary of Analyses for Severe Hypoglycemia.....	21
Table ITSZ.6.5.	Outcome Measures of CGM Data	23
Table ITSZ.6.6.	Guidance Recommended CGM Targets of Glycemic Control	24

Table of Contents

Figure

Page

Figure ITSZ.5.1. Illustration of study design for Clinical Protocol I8B-MC-ITSZ..... 10

Table of Contents

Appendix		Page
Appendix 1.	Derivation of CGM Variables.....	30

3. Revision History

This statistical analysis plan (SAP) is the first version and is based on the protocol of I8B-MC-ITSZ approved on 08 June 2020 and the amendments (a) approved on 12 July 2020. SAP Version 1 was approved prior to the first visit when a subject receives study drug or any other protocol intervention.

4. Study Objectives

Table ITSZ.4.1 shows the objectives and endpoints of the study.

Table ITSZ.4.1. Objectives and Endpoints

Objectives	Endpoints
Primary	
To evaluate the time that glucose values are within the target range 70 to 180 mg/dL from CGM use, after 35 days of using the study titration scheme with LY900014 treatment and degludec	Percentage of time with sensor glucose values between 70 and 180 mg/dL (both inclusive), with CGM use during the maintenance period
Secondary	
To evaluate ICR with LY900014 treatment	ICR at the end of the maintenance period
To evaluate the relationship between ICR and TDD with LY900014 treatment	ICR×TDD for the maintenance period

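### Does SAP 6.9.2 need to name one estimate, and one ICR per participant, for the comparison with the 500 Rule?

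*SAP*

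**What the plan says.** Protocol Section 9.1 poses the question: "The study will investigate if a more aggressive ICR is needed with LY900014 treatment for participants to reach the study-specific glucose target", with the 500 Rule (ICR = 500/TDD) as the comparator. Protocol Section 9.4.3 gives the method: "Relationships between ICR and TDD will be evaluated through regression lines (ICR versus 1/TDD) and compared with the" 500 Rule. SAP Section 6.9.2 repeats this by visit and adds two details: "Regression lines with and without intercept will be analyzed", and "The analyses will be conducted based upon ICR and mean total daily insulin dose (U/day) collected for Visit 3 and Visit 14, separately".

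Two endpoints bear on the same relationship. SAP Table ITSZ.4.1 lists "ICR×TDD for the maintenance period" as a secondary endpoint. Protocol Section 3 lists as exploratory "Slope of the linear regression line of ICR or ISF on the reciprocal of TDD". Section 6.9.2 does not name ICR×TDD, and Table ITSZ.6.2 has no row for it. It is reached by the general sentence "Continuous secondary efficacy variables, as well as the change from baseline for these variables, will be analyzed by the MMRM or ANCOVA model". SAP Section 6.1 then requires summary statistics, LS means and standard errors for actual values as well as changes, and sets confidence intervals at 95%.

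On meals, Section 6.9.2 promises a listing that includes "changes in ICR by meal captured during Treatment period in the eCRF". It does not say how meal-specific ICRs become the one value per participant and visit that the models need.

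**The concern.** The 500 Rule is the only outside benchmark in Protocol Section 9.1, so the reader will want one number to hold against 500. The plan offers two fits without ranking them, and their slopes behave differently. The no-intercept slope estimates the rule's constant approximately. The with-intercept slope equals the constant only if the true intercept is zero, and at n = 30 it is about three times less precise. ICR×TDD is the constant itself, participant by participant, yet no text sets it beside 500.

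If the with-intercept slope were taken as the constant, a value of 450 could look like evidence for a more aggressive ICR when the rule in fact holds. The choice of ICR adds a second freedom: a breakfast ICR and a dinner ICR can fall on opposite sides of the rule. The primary endpoint, the sample size and safety are not involved.

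**Working it through.** **The plan's own precision figure.** The documents calculate precision only for time in range. With n = 30 and SD 12%, the half-width met with 80% probability is t(0.975, 29) × SD × √[χ²(0.80, 29)/29] / √30 = 2.045 × 12 × √(35.14/29) / √30 = 4.93%, as stated in SAP Section 5.2. Dropout: 30/0.90 = 33.3, so 34. There is no error here, and n = 30 carries forward.

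**What a line says about the rule.** A fitted line is ICR = a + b/TDD. Multiplying by TDD gives the constant that the line implies at a given dose: b + a × TDD. The rule is a = 0 and b = 500 jointly. Reading b alone discards the a × TDD term.

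**Why the slope alone is imprecise.** For equal error variance, SE(no intercept)/SE(with intercept) = √[Σ(x − x̄)²/Σx²], with x = 1/TDD. If x has a CV of 35% (assumed), this is about √[0.1225/1.1225] = 0.33, a threefold difference. Errors in a and b run in opposite directions, so they largely cancel when the line is read near the middle of the data.

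**Simulation with the rule exactly true.** Assumptions, since the documents give none: n = 30, median TDD 45 U/day, between-person CV 35–45%, ICR scatter 15%, TDD scatter 0, 5 or 10%. In case A TDD does not respond to ICR; in case B half of TDD does.

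| Quantity read against 500 | Mean | SD |
|---|---|---|
| With-intercept slope alone | 462–530 | 27–66 |
| With-intercept line at TDD 45 (b + 45a) | 504–506 | 7–18 |
| No-intercept slope | 498–508 | 9–23 |
| Geometric mean ICR×TDD | 500–502 | 7–16 |

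The two slopes differ by more than 50 in 18–46% of trials in case A and 3.5–21% in case B. The with-intercept slope is at or below 450 in 14–44% (A) and 0.2–22% (B). By contrast, the no-intercept slope and the geometric mean differ by more than 50 in at most 0.6% of trials, and by more than 25 in at most 11%.

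**When the rule's form is right but the constant is 400.** With TDD log-SD 0.35 and ICR log-SD 0.2, the with-intercept fit averages b = 400.1 and a = −0.01. At TDD 45 the line gives 400.1 − 0.01 × 45 = 399.7, against 399.6 for both the no-intercept slope and mean ICR×TDD.

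**When the rule's form is wrong.** Let ICR vary as TDD^−0.7, with ICR×TDD = 500 at TDD 45 and ICR log-SD 0.2. Mean ICR×TDD is 503 and the no-intercept slope 469. The with-intercept fit is b = 337.5, a = 3.49. Its line implies 337.5 + 3.49 × 30 = 442 at TDD 30, 337.5 + 3.49 × 45 = 495 at TDD 45, and 337.5 + 3.49 × 65 = 564 at TDD 65. The product alone would suggest that the rule holds; the with-intercept line shows that it does not.

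**ICR by meal (spread assumed).** If breakfast ICR is a fraction d below lunch and dinner and the three-meal mean gives 500, breakfast gives 500 × 3(1 − d)/(3 − d) and the other meals 500 × 3/(3 − d). For d = 0.1, 0.2 and 0.3 these are 466, 429 and 389 against 517, 536 and 556. Averaging rules differ far less: with TDD 45 and ICRs of 8, 10 and 12, the arithmetic mean gives 10 × 45 = 450 and the harmonic mean 438, whereas single meals give 360 to 540.

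**The case for a change.** The best case for a change is that exploratory status does not excuse leaving open which number answers a stated question, and that two reported numbers that can disagree invite a choice after the data are seen. A few SAP lines and one small table would settle it from data already collected. A t interval for mean ICR×TDD also behaves better: with the rule true and ICR log-SD 0.2 to 0.3 it excludes 500 in 5–6% of trials, against 12–15% for ordinary least-squares slope intervals.

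Part of this stands. The SAP does not name the summary to be read against 500, and it has no rule for combining ICRs across meals. A programming specification must supply both.

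The rest is weaker. The SAP compares lines with the rule, and a line includes its intercept; the large disagreement arises only when that intercept is dropped. Both fits are to be produced, so neither can be quietly left out. Mean ICR×TDD with its standard error is already due as a secondary endpoint, and any reader can place it beside 500. No formal test against 500 is planned, so the interval error rates describe a decision that the plan does not make. Nor is the proposed headline clearly better: where the rule's form fails, the product can sit at 503 while the planned lines reveal the failure.

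**Conclusion.** No change is needed. The text gaps are real, but they are details that an analyst fills in the ordinary course: read the with-intercept fit as a whole line, set the no-intercept slope and mean ICR×TDD beside 500, and use one consistently defined ICR per participant and visit. Read that way, the planned outputs average 498–508 when the rule is true. The means of 462–530 and SDs of 27–66 apply only to a slope taken without its intercept.

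The meal question is the larger open item, because single-meal readings could shift the constant by up to about 22% (389 against 500) at an assumed 30% spread. The documents do not say how far meal ICRs differ, and the planned listing will show the changes by meal.

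All simulated figures rest on assumed TDD and ICR distributions. The comparison is descriptive, in a pilot that is not strictly powered even for its primary endpoint, and nothing here touches that endpoint, the sample size or safety.

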6.9.3. Exploratory Efficacy Analyses

Continuous exploratory efficacy variables, as well as the change from baseline for these variables, will be analyzed by the MMRM or ANCOVA model as described in Section 6.1, unless otherwise specified.

The following analyses will be conducted based upon ISF (mg/dL per insulin unit), mean total daily basal dose (U/day), mean total daily insulin dose (U/day), and weight (kg) collected for Visit 3 and Visit 14, separately. Relationships between the following endpoints will be explored through regression lines (King et al. 2007a, 2007b) by visit, separately. Regression lines with and without intercept will be analyzed.

- ISF and 1/TDD
- TBD and weight

The ICR (grams per insulin unit) and ISF (mg/dL per insulin unit) data from the day before a scheduled visit will be transcribed in eCRF at Visit 2, Visit 3 through Visit 14 and ET Visit, respectively. Relationships between ICR and ISF will be explored through regression lines with and without intercept by scheduled visit, separately.

The ISF and DIA data from the day before a scheduled visit will be transcribed in eCRF at Visit 2, Visit 3 through Visit 14 and ET Visit, respectively. Any changes for ISF and DIA during the Treatment period will be captured. A listing will be provided to include ISF and DIA data collected at Visit 2, changes in ISF and DIA by meal captured during treatment period in the eCRF. An MMRM model similar to that for the primary endpoint will be used to analyze actual and change from baseline in ISF and DIA, respectively.

Actual and change from baseline in fructosamine, HbA1c and 1,5-AG will be summarized and analyzed by ANCOVA.

In addition, CGM outcomes that are not included in the primary and secondary efficacy endpoints will be analyzed as exploratory efficacy endpoints. Details for the CGM analyses can be found in Section 6.13.

6.10. Safety Analyses

6.10.1. Extent of Exposure

Duration of exposure to study drug will be summarized based upon eCRF data. The following summary statistics will be provided: n, mean, SD, median, minimum, maximum, and sum (that is, total patient-years of exposure). The number and proportion of patients falling into the following different exposure categories will also be summarized: <14 days (>0 and <14 days), ≥14 and <35 days, ≥35 and <46 days, and ≥46 days.

Patients who complete the study treatment period are required to complete a safety follow-up visit without study drug; and patients who discontinue the IP unplanned are required to discontinue from the study (ITSZ Protocol 7.1).

6.10.2. Adverse Events

Events that are newly reported after the first dose of IP or reported to worsen in severity from baseline will be considered TEAEs. Events that continue during more than 1 study period (lead-in, Treatment, and safety follow-up period) with the same severity will only be counted once for the first study period.

Analyses of AEs will be descriptive and include all data collected during the treatment period. Adverse events during the lead-in period and the safety follow-up period will be provided in a listing.

The MedDRA lowest level term (LLT) will be used in the treatment-emergent assessment. The maximum severity for each LLT during the baseline period will be used as baseline severity.

In an overview table, the number and percentage of patients who experienced a TEAE, experienced a serious adverse event (SAE), died due to an AE, and discontinued from study due to an AE will be summarized.

The number and percentage of patients with SAEs and who discontinued from the study due to an AE will be summarized using MedDRA PT nested within SOC if any such events occurred. The number and percentage of patients with TEAEs will be summarized using MedDRA PT nested within SOC. Events will be ordered by decreasing frequency within SOC.

The number and percentage of patients who experienced a SAE including deaths and SAEs temporally associated or preceding deaths will be summarized using MedDRA PT (without regard to SOC). Events will be ordered by decreasing frequency within SOC. A listing of all SAEs (including data collected during lead in and the safety follow-up period) will also be provided.

The number and percentage of patients who discontinued from study in Treatment period due to an AE will be summarized using MedDRA PT (without regard to SOC). Events will be ordered by decreasing frequency. A listing of all AEs as reason for study discontinuation will also be provided.

For events that are gender-specific (as defined by MedDRA), the denominator and computation of the percentage will include only patients from the given gender. The number and proportion of patients with at least 1 event for each type of event will also be summarized.

[Table ITSZ.6.3](#) summarizes the planned analyses and the requirement of analysis data for different analysis periods.

Table ITSZ.6.3. Adverse Event Analysis Periods

Analysis Period	Analysis Population	Analysis	IP USE	Treatment
Lead-in Period	Enrolled Population	Listing: All AE including SAEs and discontinuation due to AE	N/A	Humalog
Treatment Period (Titration and Maintenance periods)	Treated Population	AE overview; TEAE by SOC and by PT;; SAE; discontinuation due to AE	Yes	LY900014
Treatment Period (Titration and Maintenance periods) and Safety Follow-up Period	Treated Population	AE overview; TEAE by SOC; SAE; discontinuation from study due to AE;	All data regardless of IP use	LY900014

Abbreviations: AE = adverse event; IP = investigational product; N/A = not applicable/available; PT = preferred term; SAE = serious adverse event; SOC = system organ class; TEAE = treatment-emergent adverse event.

